9.2.1.2 Index Date

Depending on the date of first evidence of AF over the study period, AF patients will be included at the following dates:

- On 1st January 2016 for **prevalent AF patients** (i.e., patients diagnosed AF during the historical period);
- On the first date of evidence of AF (first date of diagnosis of AF identified either by a LTD or the start date of a hospitalization, or the first date of OAC dispensation) for **incident AF patients**.

A patient will be considered exposed to OAC at the time of his/her inclusion if at least one dispensation of OAC is issued within 30 days after inclusion (including date of inclusion). In such a case, the index date will be the date of the first dispensation of OAC (cf. Appendix 1).

Otherwise, if no dispensation of OAC will be identified within 30 days from inclusion, the index date will be the date of inclusion.

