9.2.1.4 Follow-up and Censoring

[figure not shown]
The Follow-up period starts at index date and ends on the date of occurrence of one of the following events:

- Death;
- End date of the study fixed to December 31st, 2019 or to December 31st, 2020 for sensitivity analyses;

- Date of the last reimbursement of care recorded in the SNDS (patients with no consumption or reimbursement of care in the 12 months following the date of last consumption).

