9.4.2 *Derived Variables for the Primary Objective*

The incidence rate for each event of interest (stroke, major bleeding and death) in AF incidents patients between 2016 and 2019 will be derived by treatment exposure sequence and by unexposed sequence, for overall and by sub-populations (see section 9.2.3.4).

First the treatment exposure sequences will be derived (Table VII). A patient could have several lines i.e., one line by patient by treatment sequence.

Table VII. Derived variables for identification of treatment exposure or unexposed sequences

Variable	Definition
Start date of treatment sequence	
Date variable
 
Equals to the date of the first delivery of each specific treatment (VKA, Apixaban, Rivaroxaban or Dabigatran) of the sequence
 
ATC codes: B01AA, B01AF02, B01AF01, B01AE07 (respectively)

End date of treatment sequence	
Date variable
 
The end date of treatment sequence is defined as:
 
 – The day before the date of first delivery of another OAC if the patient switches to another OAC 
OR

	
 – Date of the last delivery of treatment sequence supplemented by 30 days (treatment duration), at the condition that there is no other OAC reimbursement in the next 60 days 
ATC codes: B01AA, B01AF02, B01AF01, B01AE07
 
For sensitivity analyses: duration of 30 days and 90 days of maximal number of days allowed for being refilled will be considered.

Treatment sequence	
Category variable (VKA / Apixaban / Rivaroxaban / Dabigatran)
 
Equals to “VKA / Apixaban / Rivaroxaban / Dabigatran” if the patient has a reimbursement of VKA, Apixaban, Rivaroxaban or Dabigatran during the treatment sequence
 
ATC codes: B01AA, B01AF02, B01AF01, B01AE07(respectively)

Start date of unexposed sequence	
Date variable
 
The start date of unexposed sequence is defined as:
 
 – The index date for AF patients without an OAC reimbursement in 30 days after the index date (for sensitivity analyses, the inclusion date will be the index date for all incident patients, whether or not patients received OAC therapy within 30 days of the inclusion date) 
OR
 
 – The day after the End date of treatment sequence if the patient has stopped an OAC (at the condition that there is no other OAC reimbursement in the next 60 days, period defined as “the grace period”)

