End date of unexposed sequence	
Date variable
 
The end date of unexposed sequence is defined as:
 
 – The day before the Start date of treatment sequence if the patient starts an OAC 
OR
 
 – End of follow-up period in other cases

Second, each event of interest with the occurred dates available in the data extraction for the AF patients in France during their follow-up will be derived by treatment exposure sequence as indicated in [Table VIII](#).

Table VIII. Derived variables for identifying events of interest

Variable	Definition
Stroke (ischemic or hemorrhagic)	
Binary variable (Yes / No)
 
Equals to “Yes” if the patient is hospitalized with any discharge diagnosis (i.e., main, related or associated diagnosis) of stroke (ischemic or haemorrhagic)

	
ICD-10 codes: I60.x, I61.x, I62.9, I63.x, I64.x, G45.x, G46.x, G81.x, S06.4, S06.5, S06.6
 
Equals to “No” in other cases

Major bleeding	
Binary variable (Yes / No)
 
Equals to “Yes” if the patient is hospitalized with any discharge diagnosis (i.e., main, related or associated diagnosis) of major bleeding
 
ICD-10 codes: I60.x, I61.x, I62.9, S06.4, S06.5, S06.6, I85.0, K22.6, K25.0, K25.2, K25.4, K25.6, K26.0, K26.2, K26.4, K26.6, K27.0, K27.2, K27.4, K27.6, K28.0, K28.2, K28.4, K28.6, K29.0, K62.5, K92.0, K92.1, K92.2, D62, H35.6, H43.1 H45.0, H92.2, I31.2, J94.2, R04.x, K66.1, M25.0, N02, N93.8, N93.9, N95.0, R31, R58, T79.2
 
Equals to “No” in other cases

Death	
Binary variable (Yes / No)
 
Equals to “Yes” if the date of death is reported in DCIR
 
Equals to “No” in other cases

Date of occurrence	
Date variable
 
Equals to the value of date when occurred the event

In the case of a patient presents an event of interest during the grace period, which ends after the end of the study, the event will be considered neither in an exposed nor in an unexposed period, and the patient will be censured at the end of the study period.

Then, the variable presented in [Table IX](#)[Table X](#) will be derived for the analyses of incidence, for each patient, for each event of interest and for each exposure treatment sequence.

Table IX. Derived variables for the analyses of incidence rate on events of interest

Variable	Definition

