Number of occurrences	
Continuous variable
 
Equals to the number of occurrences where the two criteria are met:
 
 – The variable of the specified event of interest (Stroke, Major bleeding or Death) equals “Yes” – The value of the variable Date of occurrence falls in the specific OAC treatment sequence period for exposed patient and during unexposed sequence period for unexposed patient 
In

And finally, the following variables in [Table X](#) will be derived for all patients selected in the study population.

Table X. Derived variables for study population

Variable	Definition
Incident AF patient	
Binary variable (Yes / No)
 
Equals to “Yes” if:
 
 – The patient is newly diagnosed AF during the inclusion period (i.e. no AF diagnostic during the historical period) 
AND
 
 – No reported events of interest (stroke, major bleeding, and death) between the inclusion date and the first date of OAC delivery among AF patients with at least one dispensation of OAC identified within 30 days from inclusion date (cf. 9.2.3.1. Inclusion Criteria) 
Equals to “No” in other cases
 
Sensitivity analyses on incidence rate of stroke, major bleeding and death, and comparison of these events in regression analyzes will be performed on all newly diagnosed AF during the inclusion period (i.e. no exclusion of patients with reported events of interest between inclusion date and index date among those with at least one dispensation of OAC identified within 30 days from inclusion date).

Gender	
Binary variable (Female / Male)
 
See Table IIIError! Reference source not found.

Age	
Categorical variable (<65 years old / 65-74 / 75-79 / ≥80 years old)
 
See Table III

Death	
Binary variable (Yes / No)
 
See Table III

Lost to follow-up	
Binary variable (Yes / No)
 
Equal to “Yes” if the patient has no consumption or reimbursement of care in the 12 months following the date of last consumption
 
Equals to “No” in other cases

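### A stroke or bleeding code on the stay that first identifies AF can count as an outcome in unexposed patients, but excludes patients dispensed an OAC within 30 days

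*SAP*

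**What the plan says.** The rules are spread over several SAP sections.

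- **Inclusion date (9.2.1.2).** For incident patients it is the first evidence of AF: "first date of diagnosis of AF identified either by a LTD or the start date of a hospitalization", or the first OAC dispensation.
- **Index date (9.2.1.2).** With an OAC dispensed within 30 days, the index date moves to that dispensation. "Otherwise, if no dispensation of OAC will be identified within 30 days from inclusion, the index date will be the date of inclusion".
- **Follow-up (9.2.1.4).** "The Follow-up period starts at index date and ends on the date of occurrence of one of the following events". No blanking period is stated.
- **Unexposed sequence (9.4.2, Table VII).** Its start is "The index date for AF patients without an OAC reimbursement in 30 days after the index date".
- **Outcomes (9.4.2, Table VIII).** Stroke is present if the patient "is hospitalized with any discharge diagnosis (i.e., main, related or associated diagnosis) of stroke (ischemic or haemorrhagic"). Major bleeding is present if the patient "is hospitalized with any discharge diagnosis (i.e., main, related or associated diagnosis) of major bleeding". The AF-identifying stay is not carved out. The date of occurrence is defined only as: "Equals to the value of date when occurred the event". Table IX counts an event if its date falls in the exposed or unexposed sequence.
- **Exclusion (9.4.2, Table X).** An incident patient must have no event "between the inclusion date and the first date of OAC delivery among AF patients with at least one dispensation of OAC" within 30 days of inclusion. Sections 9.2.3.3.2, 9.7.3.1 and 9.7.4.2 word the exclusion as events in the 30 days before the index date. Appendix 3, section 3.2, words it as no event from inclusion to index date.

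**The concern.** For a patient never dispensed an OAC, or dispensed after day 30, one admission date serves as inclusion date, index date, start of follow-up and start of unexposed time. A patient admitted with a stroke and found to be in AF during that stay would then have the stroke counted as an outcome in unexposed time, although it was already present at cohort entry. The same patient, if dispensed on day 10, would be removed from the longitudinal analyses.

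This reaches the primary objective (event rates in exposed and unexposed patients) and secondary objective 3 (their comparison). The error is systematic, so a cohort of around a million patients does not reduce it. Filling the gap on unexposed patients is the study's stated rationale.

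**Working it through.** **Rule trace.** Let day 0 be admission to the stay carrying the AF code, and date the stroke or bleeding code at day 0 (admission) or day 6 (an assumed discharge). Diagnoses carry no date of their own: Protocol Appendix 1 and SAP 9.3.1.2 list only entry and discharge dates for stays.

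| First OAC | Index day | Code dated day 0 or day 6 |
|---|---|---|
| never | 0 | counted as unexposed event |
| day 45 | 0 | counted as unexposed event |
| day 30 | 30 | patient excluded |
| day 10 | 10 | patient excluded |

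If 'between' in Table X leaves out day 0, the 30-day look-back of 9.2.3.3.2 still removes the dispensed patient. In the unexposed patient that look-back ends before the admission, so it does not reach the code.

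Two readings change the picture:

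- *Discharge dating, OAC filled on the discharge day.* If 'between' leaves that day out, the code becomes an exposed event.
- *Admission dating, with the Appendix 3 section 3.2 wording taken to include the index day.* Both groups then lose these patients.

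History variables do not settle it. Previous stroke (Table V) and history of major bleeding (Table VI) include the index date, but nothing says a code used as history is dropped as an outcome. A bleeding code in associated position is an outcome in Table VIII but not history in Table VI, which takes main or related diagnoses only.

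**Size.** The plan gives no figure to reproduce, so every input is an assumption: stroke rate λ = 0.03 per person-year in both groups (no OAC effect), follow-up U uniform on 0 to 4 years, 65% of hospital or LTD entrants dispensed within 30 days, and a stroke code on a share p of inclusion stays.

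Upper case in closed form (all enter by hospital stay, no switching):

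- r = 1 − E[exp(−λU)] = 1 − (1 − e^(−0.12))/0.12 = 0.0577
- Person-years per patient = r/λ = 1.922
- Unexposed rate = [p + (1−p)r] / [(1−p) × 1.922]
- At p = 1%: (0.01 + 0.99 × 0.0577)/(0.99 × 1.922) = 0.0671/1.903 = 0.0353, and 0.0353/0.03 = 1.18

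Sensitivity analysis 1 (9.7.6), same case, with an assumed 15 unexposed days before dispensing:

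- Rate = [p + (1−p)(0.35r + 0.65λ × 15/365.25)] / [(1−p)(0.35 × 1.922 + 0.65 × 15/365.25)]
- At p = 1%: 0.0308/0.6925 = 0.0444, ratio 1.48

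The other cases are from Monte Carlo simulation (1.5 million patients per cell; 0.7 million for Cox), with OAC starting and stopping at 0.3 per year each. '50/50' means half enter by hospital stay and half by LTD.

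| Unexposed/exposed ratio (truth 1) | p = 1% | 2% | 5% | 10% |
|---|---|---|---|---|
| 50/50 entry | 1.07 | 1.15 | 1.37 | 1.75 |
| 35% hospital, 35% LTD, 30% first dispensation | 1.06 | 1.12 | 1.29 | 1.62 |
| All hospital, no switching | 1.18 | 1.35 | 1.91 | 2.93 |
| As above, person-time not stopped at event | 1.16 | 1.33 | 1.82 | 2.63 |
| Sensitivity analysis 1, 50/50 | 1.20 | 1.39 | 2.01 | 3.12 |
| Sensitivity analysis 1, all hospital | 1.48 | 1.97 | 3.51 | 6.30 |
| Crude Cox HR, 50/50, event placed at half a day | 1.10 | 1.19 | 1.42 | 1.87 |
| Discharge dating, half of dispensed fill that day, 50/50 | 1.02 | 1.04 | 1.10 | 1.15 |

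In the 50/50 case the unexposed rate is 3.2, 3.4, 4.1 and 5.3 per 100 person-years against 3.0 in the exposed. In the last row the ratio is nearly right, but the exposed rate is itself too high, at 3.1, 3.3, 3.8 and 4.6.

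The ratio is 0.99–1.02 if admission-dated codes exclude both groups, and the crude HR is 0.99–1.00 if the Cox program drops day-0 events. In that second case the rate tables and the Cox models count different events.

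**The case against.** The strongest reply is that the rule may exist where it cannot be read. Section 9.2.1.2 refers to Appendix 1, whose design diagram is not shown, and the Table IX cell on which events count breaks off mid-sentence. Appendix 3, section 3.2, describes the population for the rates and Cox models without limiting the exclusion to dispensed patients; read to include the index day, with admission dating, it removes the asymmetry. This stands as a possibility. It is not stated, it would miss a discharge-dated code, and Table X ties similar wording expressly to patients dispensed within 30 days.

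For sensitivity analysis 1, section 9.2.1.2 treats a patient dispensed within 30 days as exposed from inclusion, which would make the early codes exposed events. However, the sensitivity note in Table VII sits under the start of the unexposed sequence and makes inclusion the index date for all incident patients. That supports the reading used above.

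Several limits do stand. All sizes rest on assumed inputs, and the largest on all-hospital entry, which the LTD and OAC-algorithm routes contradict. No bleeding illustration is given. The hazard ratios are crude and against all exposed time, whereas the plan uses VKA as reference and adjusts for stroke and bleeding history. No effect on DOAC-versus-VKA contrasts is shown. Symmetric exclusion would also remove the asymmetry, although it would discard patients with a previous stroke, a subgroup the study wants to analyse.

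**Conclusion.** The concern holds on the readable text and should be fixed before programming. The stated rules allow inclusion-stay stroke and bleeding codes to count as unexposed events while excluding dispensed patients who carry the same code. No readable rule prevents it. Where the codes count, the unexposed rates are biased upward for any non-zero share of such stays.

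The size is not derivable from the documents. With mixed entry and switching, the illustrative stroke rate ratio is about 1.06 to 1.75 for code shares of 1 to 10%. It is close to 1 only under readings the SAP does not state. Sensitivity analysis 1 does not repair the problem for stroke and bleeding and tends to enlarge it. Confidence is medium, because a diagram that is not shown may contain a history-only rule.

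**What to change.** Amend Tables VIII and X and sections 9.2.3.3.2, 9.7.3.1 and 9.7.4.2, with the same rule for sensitivity analysis 1 in 9.7.6:

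1. Treat stroke and bleeding codes on the inclusion stay as history only, in exposed and unexposed patients alike: never an outcome and never a ground for exclusion. Add associated diagnoses to history of major bleeding in Table VI, so that the bleeding codes removed as outcomes are kept as history.
2. Define the date of occurrence of stroke and bleeding as the admission date of the stay carrying the code.
3. Keep deaths during the inclusion stay as events. Report the number of inclusion stays with a stroke or bleeding code by exposure group.

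With these rules the simulated ratio is 0.99–1.01, also in sensitivity analysis 1. Moving the principal time zero is optional and not needed for this defect.

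The cost is SAP wording and programming on data already being extracted. There are four losses:

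- New strokes or bleeds arising during the inclusion stay are not counted, so there are fewer unexposed events.
- A transfer stay repeating the code still counts unless it is joined to the inclusion stay.
- Widening the bleeding history changes a stratifier and a confounder.
- Events after the inclusion stay but before dispensing would still exclude only dispensed patients.

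If the Appendix 1 diagram already contains such a rule, writing it into the tables costs almost nothing.

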9.4.3 Derived Variables for the Secondary Objectives

9.4.3.1 To describe the characteristics of AF patients exposed and unexposed to OAC

The sociodemographic characteristics, comorbidities, medical history of interest and concomitant treatments (respectively [Table XII](#), [Table XIII](#) and [Table XIV](#)) will be derived at start follow-up date for AF incident patients exposed and unexposed to OAC ([Table XI](#)).

Table XI. Derived variables for exposition to OAC

Variable	Definition
Exposed to OAC at index date	
Binary variable (Exposed to OAC/Unexposed to OAC)
 
Equals to ‘Exposed to OAC’ if the patient has at least one delivery of AOC (VKA, Apixaban, Dabigatran or Rivaroxaban) at index date (defined in 9.2.1.4)
 
ATC codes: B01AA, B01AF02, B01AF01, B01AE07
 
Equals to ‘Unexposed to OAC’ if the patient has no reimbursement for AOC at index date (defined in 9.2.1.4)Table III

Treatment at index date	
Categorical variable (VKA/Apixaban/Dabigatran/Rivaroxaban/Unexposed)
 
Equals to “VKA” if the patient has one reimbursement of VKA at -index date
 
Equals to “Apixaban” if the patient has one reimbursement of Apixaban at index date
 
Equals to “Dabigatran” if the patient has one reimbursement of Dabigatran at index date
 
Equals to “Rivaroxaban” if the patient has one reimbursement of Rivaroxaban at index date
 
Equals to “Unexposed” if the patient has any reimbursement of OAC at index date

Table XII. Derived variables for the sociodemographic characteristics

Variable	Definition
Age	
Continuous variable (year)
 
See Table III

Sex	
Binary variable (Female / Male)
 
See Table III

Complimentary universal health care (CMU-c)	
Binary variable (Yes / No)
 
Equals to “Yes” if the patient benefits from an exemption from care on the grounds of CMU-c for care received on the index date
 
Equals to “No” in other cases

Aid for complementary health care (ACS) for elderly patients	
Binary variable (Yes / No)
 
Equals to “Yes” if the patient benefits from an aid for complementary health care on the index date
 
Equals to “No” in other cases

Region of residence	Categorical variable (Île de France, Centre-Val de Loire, Corse, etc.) Derived based on the code of the department of residence recorded with health cares carried out on index date
Frail patient	Binary variable (Yes / No) See Table VI
Modified CHAD₂DS₂VASC score strata	Categorical variable (Low / Moderate / High) See Table VI
Hypertension (for HAS-BLED score derivation)	Binary variable (Yes / No) See Table VI
Abnormal renal (for HAS-BLED score derivation)	Binary variable (Yes / No) Equals to “Yes” if the patient is hospitalized with any discharge diagnosis (i.e., main, related or associated diagnosis) of renal failure on or in the 2 years prior to the index date: ICD-10 codes: N17-N19 OR Equals to “Yes” if the patient is covered by the LTD status for renal failure at least one day ICD-10 codes: N17- N19 OR Equals to “Yes” if the patient has received dialysis sessions CCAM codes: JVJF004, JVJF008, JVRP004, JVJB001, JVRP007, JVRP008, YYYY007 PRS codes : 2121, 2122, 2123, 2126, 2129, 2131, 2132, 2134, 2135, 2136, 2139, 2147, 2334, 2124, 2125, 2127, 2128, 2137, 2138, 2140, 2142, 2143, 2144, 2145, 2146 GHM codes : 11K021, 11K022, 11K023, 11K024, 11K02J, 28Z03Z, 28Z04Z, 28Z01Z, 28Z02Z Equals to “No” in other cases
Liver function (for HAS-BLED score derivation)	Binary variable (Yes / No) Equals to “Yes” if the patient is hospitalized with any discharge diagnosis (i.e., main, related or associated diagnosis) of chronic hepatic disease on or in the 2 years prior to the index date: ICD-10 codes: K70-K77 OR

	
Is covered by the LTD status for chronic hepatic disease at least one day
 
ICD-10 codes: K70- K77
 
Equals to “No” in other cases

Previous Stroke (for HAS-BLED score derivation)	
Binary variable (Yes / No)
 
Equals to “Yes” if the patient is hospitalized with any discharge diagnosis (i.e., main, related or associated diagnosis) of ischemic/undefined stroke or transient ischemic attack (TIA) on or in the 2 years prior to the index date:
 
ICD-10 codes: I63, I64, G45, G46, G81
 
OR
 
Is covered by the LTD status for stroke at least one day
 
ICD-10 codes: I63, I64, G45, G46, G81
 
Equals to “No” in other cases

Bleeding history or predisposition (for HAS-BLED score derivation)	
Binary variable (Yes / No)
 
Equals to “Yes” if the patient is hospitalized with hospital-discharge summary with primary diagnosis of bleeding on or in the 2 years prior to the index date:
 
ICD-10 codes: D62, D683, D698, D699, H113, H313, H356, H431, H450, H922, I230, I312, I600-I616, I618-I621, I629, I850, I983, J942, K250, K252, K254, K256, K262, K264, K270, K272, K274, K276, K280, K282, K284, K286, K661, K920, K921, K922, M250, N020-N029, N421, N920, N921, N923, N924, N938, N939, N950, R040, R041, R042, R048, R049, R31, R58, S064, S065, S066, S260, S271, T792
 
Equals to “No” in other cases

Labile international normalized ratio (INR) (for HAS-BLED score derivation)	
Binary variable (Yes / No)
 
Not applicable to SNDS data (INR results are not captured in SNDS databases).

Elderly (for HAS-BLED score derivation)	
Binary variable (≤ 65 years old / > 65 years old)

Drugs predisposing to bleeding or alcohol concomitantly (for HAS-BLED score derivation)	
Binary variable (Yes / No)
 
Variable Drugs equals to “Yes” if the patient has at least one drug dispensation for antiplatelet agents (acetylsalicylic acid: B01AC06 ATC code, clopidogrel: B01AC04 ATC code) or NSAIDs (M01A ATC code) in the 4 months before the index date.
 
OR

	
Variable Alcohol equals to “Yes” if the patient is hospitalized with any discharge diagnosis (i.e., main, related or associated diagnosis) of all causes related to alcohol on or in the 2 years prior to the index date:
 
ICD-10 codes : E244, E512, F10, G312, G621, G721, I426, K292, K70, K860, R780, T51, X45, X65, Y15, Y90, Y91, Y573, Z502, Z714, Z721.
 
Equals to “No” in other cases

HAS-BLED score	
Continuous variable (between 1 and 9)
 
Derived based on (19)
 
Equals to sum of:
 
 ○ 1 point if the variable Hypertension equals to “Yes” ○ 1 or 2 points if the variable Abnormal renal and liver function equals to “Yes” (1 point each) ○ 1 point if the variable Stroke equals to “Yes” ○ 1 point if the variable Bleeding equals to “Yes” ○ 1 point if the variable Labile INRs equals to “Yes” ○ 1 point if the variable Elderly equals to “>65 years old” ○ 1 or 2 points if the variable Drugs or alcohol equals to “Yes” (1 point each)
Contraindications to OAC	
Binary variable (Yes/No)
 
Equals to “Yes” if the patient presents at least one contraindication to OAC among the followings:
 
 ● End-stage renal disease on dialysis ● Diseases of the blood and blood-forming organs ● Certain disorders involving the immune mechanism ● Recent history of acute bleeding gastric or duodenal ulcer ● Hepatic cirrhosis or fibrosis or liver failure 
Equals to “No” in other cases.

Chronic renal disease (for contraindications to OAC)	
Binary variable (Yes / No)
 
Equals to “Yes” if the patient meets any criterion below on or in the 2 years prior to the index date:
 
 – A main or related discharge diagnosis of renal transplantation 
ICD-10 code: Z94.0
 
OR

- A renal transplantation surgery
CCAM: JAEA003, HNEA002
 OR
- Is hospitalized at least once with any diagnosis (i.e., main, related or associated diagnosis) of chronic renal disease
ICD-10 codes: N18.x
 OR
- Is covered by the LTD status for chronic renal disease at least one day
ICD-10 codes: N18.x
 OR
- Has received ≥ 19 hemodialysis sessions in inpatient or outpatient settings
CCAM codes : JVJF004, JVJF008, JVRP004
PRS codes : 2121, 2122, 2123, 2126, 2129, 2131, 2132, 2134, 2135, 2136, 2139, 2147, 2334
GHM codes : 11K021, 11K022, 11K023, 11K024, 11K02J, 28Z03Z, 28Z04Z
 OR
- Has received ≥ 1 peritoneal dialysis session in inpatient or outpatient settings
CCAM codes: JVJB001, JVRP007, JVRP008, YYYY007
PRS codes : 2124, 2125, 2127, 2128, 2137, 2138, 2140, 2142, 2143, 2144, 2145, 2146
GHM codes : 28Z01Z, 28Z02Z

Equals to "No" in other cases.

Chronic renal disease requiring dialysis (for contraindications to OAC)	Binary variable (Yes / No) Equals to "Yes" if the patient meets any criterion below on or in the 2 years prior to the index date: 
 - Has the value "Yes" for the variable Chronic renal disease AND - Has at one reimbursement for a dialysis session performed at hospital or in outpatient settings CCAM codes: JVJB001, JVJF004, JVJF008, JVRP004, JVRP007, JVRP008, YYYY007
--	---

	
PRS codes : 2121, 2122, 2123, 2124, 2125, 2126, 2127, 2128, 2129, 2131, 2132, 2133, 2134, 2135, 2136, 2137, 2138, 2139, 2140, 2142, 2143, 2144, 2145, 2146, 2147, 2334
 
GHM codes : 28Z01Z, 28Z02Z, 28Z03Z, 28Z04Z, 11K021, 11K022, 11K023, 11K024, 11K025
 
Equals to “No” in other cases

Diseases of the blood and blood-forming organs (for contraindications to OAC)	
Binary variable (Yes/No)
 
Equals to “Yes” if the patient meets any criterion below:
 
 - Is hospitalized at least once with any discharge diagnosis (i.e. principal, related or associated diagnosis in PMSI-MSO) of disease of the blood and blood forming organs during historical period 
ICD-10 codes: D55-D77
 
OR
 
 - Is covered by the LTD status for of disease of the blood and blood forming organs ongoing at the index date 
ICD-10 codes: D55-D77
 
Equals to “No” in other cases

Diseases related to immune disorders (for contraindications to OAC)	
Binary variable (Yes/No)
 
Equals to “Yes” if the patient meets any criterion below:
 
 - Is hospitalized at least once with any discharge diagnosis (i.e. principal, related or associated diagnosis in PMSI-MSO) of diseases related to immune disorders during historical period 
ICD-10 codes: D80-D89
 
OR
 
 - Is covered by the LTD status for diseases related to immune disorders ongoing at the index date 
ICD-10 codes: D80-D89
 
Equals to “No” in other cases

Recent history of acute bleeding gastric or duodenal ulcer (for contraindications to OAC)	
Binary variable (Yes/No)
 
Equals to “Yes” if the patient meets any criterion below:
 
 - Is hospitalized at least once with any discharge diagnosis (i.e. principal, related or associated diagnosis in PMSI-MSO) of acute bleeding gastric or duodenal ulcer in the 6 months before the index date 
ICD-10 codes : K274, K254 ; K284, K264

	
OR
 
 – Is covered by the LTD status for acute bleeding gastric or duodenal ulcer ongoing at the 6 months before the index date 
ICD-10 codes : K274, K254 ; K284, K264
 
Equals to “No” in other cases

Hepatic cirrhosis/fibrosis, liver failure (for contraindications to OAC)	
Binary variable (Yes / No)
 
Equals to “Yes” if the patient meets any criterion below on or in the 2 years prior to the index date:
 
 – Is hospitalized at least once with any diagnosis (i.e., main, related or associated diagnosis) of hepatic impairment 
ICD-10 codes: K70.4, K71.1, K72.1, K72.9, K76.5, K76.6, K76.7
 
OR
 
 – Is covered by the LTD status for hepatic impairment at least one day 
ICD-10 codes: K70.4, K71.1, K72.1, K72.9, K76.5, K76.6, K76.7
 
Equals to “No” in other cases

Table XIII. Derived variables for the medical history and comorbidities

Variable	Definition
Cerebrovascular diseases (CBVD)	
Binary variable (Yes / No)
 
See Table VI

Coronary arterial diseases (CAD)	
Binary variable (Yes / No)
 
See Table V

Dementia	
Binary variable (Yes / No)
 
See Table VI

Congestive Heart failure	
Binary variable (Yes / No)
 
Equals to “Yes” if the patient is hospitalized with any discharge diagnosis (i.e., main, related or associated diagnosis) of congestive heart failure, on or in the 2 years prior to the index date
 
OR
 
Is covered by the LTD status for congestive heart failure at least one day
 
ICD-10 codes: I50.2, I50.3, I50.4
 
Equals to “No” in other cases

Peripheral arterial disease	
Binary variable (Yes / No)
 
Equals to “Yes” if the patient is hospitalized with any discharge diagnosis (i.e., main, related or associated diagnosis) of peripheral arterial disease, on or in the 2 years prior to the index date
 
OR
 
Is covered by the LTD status for peripheral arterial disease at least one day
 
ICD-10 codes: I70.0-I74, I771
 
Equals to “No” in other cases

Other vascular diseases	
Binary variable (Yes / No)
 
Equals to “Yes” if the patient is hospitalized with any discharge diagnosis (i.e., main, related or associated diagnosis) of peripheral arterial disease or is covered by the LTD status for peripheral arterial disease at least one day, in the 2 years prior to the index date
 
OR
 
Is covered by the LTD status for other vascular diseases at least one day
 
ICD-10 codes: I79.0, I79.2, K55.1, K55.8, K55.9, Z95.8, Z95.9.
 
Equals to “No” in other cases,

Sleep disorders	
Binary variable (Yes / No)
 
Equals to “Yes” if the patient is hospitalized with any discharge diagnosis (i.e., main, related or associated diagnosis) of sleep disorders, on or in the 2 years prior to the index date
 
ICD-10 codes: G47.x
 
Equals to “No” in other cases

Active cancer	
Binary variable (Yes / No)
 
See Table V

Age adjusted Charlson Comorbidity Index (ACCI) adapted to SNDS data	
Continuous variable (point)
 
See Table V

Malnutrition	
Binary variable (Yes / No)
 
See Table V

Morbid Obesity	
Binary variable (Yes / No)
 
See Table V

Anemia	
Binary variable (Yes / No)

	
Equals to "Yes" if the patient is hospitalized with any discharge diagnosis (i.e., main, related or associated diagnosis) of anemia, on or in the 2 years prior to the index date
 
OR
 
Is covered by the LTD status for anemia at least one day
 
ICD-10 codes : D50.x, D53.x
 
Equals to "No" in other cases

Chronic obstructive pulmonary disease (COPD)	
Binary variable (Yes / No)
 
Equals to "Yes" if the patient is hospitalized with any discharge diagnosis (i.e., main, related or associated diagnosis) of chronic obstructive pulmonary disease, on or in the 2 years prior to the index date
 
OR
 
Is covered by the LTD status for COPD at least one day
 
ICD-10 codes: J44.9
 
Equals to "No" in other cases

History of Diabetes	
Binary variable (Yes / No)
 
See Table V

Risk of falls	
Binary variable (Yes / No)
 
See Table V

Poly-medicated	
Binary variable (Yes / No)
 
Equals to "Yes" if the patient has reimbursements for ≥ 5 different medications (different ATC5) in the year before the index date.
 
Equals to "No" in other cases (i.e., patient with reimbursement for < 5 different medications in the year before the index date).

At least one visit to a nursing home	
Binary variable (Yes / No)
 
See Table V

History of major bleeding	
Binary variable (Yes / No)
 
See Table VI

One or more comorbidities	
Binary variable (Yes / No)
 
See Table VI

Table XIV. Derived variables for concomitant treatments

Variable	Definition
----------	------------

Beta-blockers	Binary variable (Yes / No) Equals to “Yes” if the patient has reimbursements for at least one dispensation at pharmacy of any beta-blockers, on or in the 4 months prior to the index date ATC codes: C07xxxx Equals to “No” in other cases Table V
Antihypertensives	Binary variable (Yes / No) Equals to “Yes” if the patient has reimbursements for at least one dispensation at pharmacy of any antihypertensive drug, on or in the 4 months prior to the index date ATC codes: C02xxxx, C03xxxx, C08xxxx, C09xxxx (excluding C03BA08 and C03CA01) Equals to “No” in other cases
Antiplatelet drugs	Binary variable (Yes / No) Equals to “Yes” if the patient has reimbursements for at least one dispensation at pharmacy of any antiplatelet drug, on or in the 4 months prior to the index date ATC codes: B01ACxx Equals to “No” in other cases
Other anticoagulants	Binary variable (Yes / No) Equals to “Yes” if the patient has reimbursements for at least one dispensation at pharmacy of any other anticoagulant, on or in the 4 months prior to the index date ATC codes: B01ABxx, B01AExx (except B01AE07), B01AFxx (except B01AF01 and B01AF02), B01AXxx Equals to “No” in other cases
Non-steroidal anti-inflammatory drugs (NSAIDs)	Binary variable (Yes / No) Equals to “Yes” if the patient has reimbursements for at least one dispensation at pharmacy of any NSAID, on or in the 4 months prior to the index date ATC codes: M01Axxx Equals to “No” in other cases
Oral corticoids	Binary variable (Yes / No) Equals to “Yes” if the patient has reimbursements for at least one dispensation at pharmacy of any oral corticoid, on or in the 4 months prior to the index date

	
ATC codes: H02AB
 
Equals to “No” in other cases

Proton pump inhibitors	
Binary variable (Yes / No)
 
Equals to “Yes” if the patient has reimbursements for at least one dispensation at pharmacy of any proton pump inhibitor, on or in the 4 months prior to the index date
 
ATC codes: A02BC
 
Equals to “No” in other cases

Selective serotonin reuptake inhibitor antidepressants (SSRIs)	
Binary variable (Yes / No)
 
Equals to “Yes” if the patient has reimbursements for at least one dispensation at pharmacy of any SSRI, on or in the 4 months prior to the index date
 
ATC codes: N06AB
 
Equals to “No” in other cases

Systemic azole antifungals	
Binary variable (Yes / No)
 
Equals to “Yes” if the patient has reimbursements for at least one dispensation at pharmacy of any systemic azole antifungal, on or in the 4 months prior to the index date
 
ATC codes: J02AB, J02AC
 
Equals to “No” in other cases

Medical procedure of cardioversion	
Binary variable (Yes / No)
 
Equals to “Yes” if the patient has at least one medical procedure of cardioversion, on or in the 4 months prior to the index date
 
Codes: DERP004, DERP003
 
Equals to “No” in other cases

CYP P450 inhibitors	
Binary variable (Yes / No)
 
Equals to “Yes” if the patient has reimbursements for at least one dispensation at pharmacy of any CYP P450 inhibitors, on or in the 4 months prior to the index date
 
ATC codes: B01AC24, C05AE03, C09BB10, C01BD01, J01FAxx excepted J01FA02
 
Equals to “No” in other cases

Protease inhibitors	
Binary variable (Yes / No)

	
Equals to “Yes” if the patient has reimbursements for at least one dispensation at pharmacy of any CYP P450 inhibitors, on or in the 4 months prior to the index date
 
ATC codes: J05AE
 
Equals to “No” in other cases

Antiarrhythmics	
Binary variable (Yes / No)
 
Equals to “Yes” if the patient has reimbursements for at least one dispensation at pharmacy of any antiarythmics, on or in the 4 months prior to the index date
 
ATC codes: C01BA, C01BB, C01BC, C01BD, C01BG
 
Equals to “No” in other cases

Glucose-lowering drugs	
Binary variable (Yes / No)
 
Equals to “Yes” if the patient has reimbursements for at least one dispensation at pharmacy of any glucose-lowering drugs, on or in the 4 months prior to the index date
 
ATC codes: C10AA, C10BA, C10BX; C10AB; C10AX06; C10AX13, C10AX14
 
Equals to “No” in other cases

Lipid-lowering drugs	
Binary variable (Yes / No)
 
Equals to “Yes” if the patient has reimbursements for at least 3 dispensations at pharmacy of any glucose-lowering drug, on or in the 4 months prior to the index date:
 
ATC codes: A10Axx, A10Bxx excepted for A10BX06
 
OR
 
Has reimbursements for 2 dispensations at pharmacy of any glucose-lowering drug, of which at least one in a package containing >80 pills, on or in the 4 months prior to the index date:
 
ATC codes: A10Axx, A10Bxx excepted A10BX06
 
Equals to “No” in other cases

Digitalis glycosides	
Binary variable (Yes / No)
 
Equals to “Yes” if the patient has reimbursements for at least one dispensation at pharmacy of any digitalis glycosides, on or in the 4 months prior to the index date
 
ATC codes: C01AA
 
Equals to “No” in other cases

Nitrate derivatives	Binary variable (Yes / No) Equals to "Yes" if the patient has reimbursements for at least one dispensation at pharmacy of any nitrates derivatives on or in the 4 months prior to the index date ATC codes: C01DA Equals to "No" in other cases
----------------------------	--

